10.3.1.2 Visual Index for Ichthyosis Severity – Scaling

The secondary endpoint is the number of subjects in each treatment group who experience a severity score of 0 or 1 at Day 90/EOT on the overall 16-point VIIS for scaling.

The investigator will rate the subject's condition using the 5-point VIIS for each body area (chest/abdomen, back, legs, and arms) and an overall score at each time point shown in the Schedule of Events (Section 2.2):

0	Normal skin; no perceptible scale or smoothening
1	Areas of normal skin intermixed with areas showing smoothening (diminished fine skin markings, shininess, waxiness) or small scales (visibly separated/fractured stratum corneum)
2	Confluent smoothening (diminished fine skin markings, shininess, waxiness) or small scales (visibly separated/fractured stratum corneum)
3	Confluent scales (visibly separated/fractured stratum corneum) including some large (>1 cm), thick scales
4	Confluent, primarily large, thick scales

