
CRITERIA FOR EVALUATION
	
Primary efficacy endpoint: The proportion of subjects in each treatment group who experience successful resolution of LI where “success” is defined as clear/almost clear on treated areas and at least a 2-grade change from Baseline at Day 90/end-of-treatment (EOT) in the Double-blind Period on the 5-point IGA full body scale.
 
Secondary endpoints:
 
 – The difference in mean scores between the active trifarotene cream HE1 and vehicle groups in the following assessment indices from Baseline through Day 90: 
 – 5-point Visual Index for Ichthyosis Severity (VIIS) for scaling (overall 16 points for scaling, i.e., 0-4 points for 4 body areas: chest/abdomen, back, arms, and legs) – Individual score for roughness (Scale: 0–4) – Palm/sole Assessment (Scale: 0–4) – Quality of life per Dermatology Life Quality Index (DLQI) – The difference in proportion of subjects with presence of fissures on palms/soles (presence/absence, number of fissures, and pain associated with fissures on a 0-3 scale) at Day 90 between the active trifarotene cream HE1 and vehicle groups 
Exploratory endpoints:
 
 – The difference in mean ectropion (Ectropion Severity Score [ESS] of 0–8) scores between the active trifarotene cream HE1 and vehicle groups from Baseline through Day 90 – The difference in quality of life per EQ-5D-5L score between the active trifarotene cream HE1 and vehicle groups from Baseline through Day 90 
Safety endpoints:
 
 – Reported serious adverse events (SAEs), treatment-emergent AEs (TEAEs), and changes in clinical laboratory tests, vital signs, physical examinations, and 12-lead ECGs – Local tolerability (stinging/burning, pruritus, or erythema on: 0-3 scales [none, mild, moderate, severe]) for each body area (chest/abdomen, back, legs, arms, and face/neck) 
Pharmacokinetic endpoints: Plasma concentrations of CD5789 and its major metabolites will be measured.

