	
were compliant with study drug application, and who had no significant protocol deviations.
 
The PK population includes all subjects in the Safety Population who have at least 1 plasma sample with quantifiable concentration. The PK population will be used to summarize all PK endpoints.
 
The following populations are planned for the OLE of this study:
 
The OLE Safety population: all subjects who complete the 90-day Double-blind Treatment Period and receive at least 1 application of study drug in the OLE.
 
OLE ITT population: all subjects who complete the 90-day Double-blind Period and who sign the OLE informed consent.
 
The OLE mITT population: all subjects in the OLE safety population with at least 1 assessment of efficacy after Visit 6.
 
The OLE PP population: all subjects in the OLE mITT population who met all inclusion criteria and no exclusion criteria, were compliant with study drug application from baseline through EOT, and who had no significant protocol deviations throughout the study.
 
Subject Characteristics and Disposition: Descriptive statistics will be used to summarize demographic characteristics (age, sex, ethnicity, and race) and baseline characteristics for all enrolled subjects. Medical history, physical examination findings, and vital sign measurements for all randomized subjects will be presented in listings.
 
Efficacy Analyses: The number and proportion of subjects in each treatment group with successful resolution of LI by Day 90/EOT in the Double-blind Period will be presented. The primary efficacy endpoint will be analyzed using a logistic regression model with treatment and age group as factors. Other baseline characteristics and interactions may be included. The odds ratios and 95% CIs for the odds ratios will be presented. The difference in proportions between the active trifarotene cream HEI and vehicle cream groups, 95% CIs for the differences, and P-values for the differences in treatment will also be presented.
 
The IGA scores as well as secondary and exploratory efficacy endpoints will be analyzed by visit using descriptive statistics through Day 180 (end of OLE treatment period). Change from Baseline through Day 90 will be presented and analyzed using a mixed model for repeated measures (MMRM). The model will include the change from Baseline score as the dependent variable, treatment group as a fixed effect, subject as a random effect, and Baseline score value as a covariate. Frequencies of results and 95% confidence intervals will also be reported, and scores will be analyzed as categorical variables using the Cochran-Mantel-Haenszel test. For subjects who report having fissures, the number of fissures and pain related to fissures will also be presented on a scale of 0-3 (none, mild, moderate, severe).
 
Clinical Pharmacology Analyses: Noncompartmental PK analysis will be performed for the PK subset of subjects, as data permit. Plasma concentrations of CD5789 and its major metabolites will be measured and will be listed by subject.
 
Safety Analyses: Safety and tolerability will be assessed based on the incidence of reported TEAEs, and SAEs, including relationship to study drug and severity, as well as physical examination findings, vital sign measurements (supine systolic blood pressure [SBP] and diastolic blood pressure [DBP] and pulse), clinical laboratory results (hematology, including serum aminotransferases and serum lipids, coagulation, clinical chemistry, and urinalysis) and 12-lead ECGs. Descriptive statistics for observed values and change from Baseline will be calculated at each visit within each study period and by treatment group within cohort.

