13.1.4.1 Efficacy Endpoints

Primary efficacy endpoint: The proportion of subjects in each treatment group who experience successful resolution of LI where “success” is defined as clear/almost clear overall and at least a 2-grade change from Baseline at Day 90/EOT in the Double-blind Period on the 5-point IGA scale.

Secondary: The secondary endpoints are as follow:

- The difference in mean scores between the active trifarotene cream HE1 and vehicle groups in the following assessment indices from Baseline through Day 90:
 - 5-point VIIS scale for scaling
 - Individual score for roughness (Scale: 0–4)
 - Palm/sole Assessment (Scale: 0–4)
 - Quality of life per DLQI
- The difference in proportion of subjects with presence of fissures on palm/soles (presence/absence, number of fissures, and pain associated with fissures [on a 0-3 scale]) at Day 90 between the active trifarotene cream HE1 and vehicle groups

Exploratory: The exploratory endpoints are as follow:

- The difference in mean ectropion scores (ESS of 0–8) between the active trifarotene cream HE1 and vehicle groups from Baseline through Day 90
- The difference in quality of life per EQ-5D-5L scores between the active trifarotene cream HE1 and vehicle groups from Baseline through Day 90

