13.1.4.3 Secondary Analyses

Secondary and exploratory efficacy endpoints will be analyzed separately for each period (Double-blind and OLE) using descriptive statistics.

Additionally, for the Double-blind Period only, change from Baseline in continuous secondary endpoints through Day 90 will be presented and analyzed using a mixed model for repeated measures (MMRM). The model will include the change from baseline score as the dependent variable, treatment group as a fixed effect, subject as a random effect, and baseline score value as a covariate.

For subjects who report having fissures, descriptive summaries of the number of fissures and pain related to fissures will also be presented by treatment group and body area for each period.

The DLQI scores will also be analyzed using descriptive statistics through Day 90.

The proportion of subjects with at least a 50% reduction in IGA score from Baseline will be analyzed using the same logistic regression analysis described in Section 13.1.4.2.

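### The VIIS secondary endpoint is defined as a 0/1 responder count in one section and as a mean difference in two others, and the 0/1 cut does not suit a four-area total; fissure number and pain also need an all-subject summary

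*Protocol*

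**What the plan says.** **VIIS.** Section 10.3.1.2 of the Protocol states: "The secondary endpoint is the number of subjects in each treatment group who experience a severity score of 0 or 1 at Day 90/EOT". The same sentence applies the cut "at Day 90/EOT on the overall 16-point VIIS for scaling". Section 13.1.4.1 lists the VIIS among the secondary endpoints under a different measure, "The difference in mean scores between the active trifarotene cream HE1 and vehicle groups in the following assessment indices from Baseline through Day 90", and names the instrument as the "5-point VIIS scale for scaling". The Synopsis also uses the mean difference and the 5-point label, but adds that the score is the "overall 16 points for scaling, i.e., 0-4 points for 4 body areas".

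For analysis, Section 13.1.4.3 assigns continuous secondary endpoints an MMRM on change from Baseline through Day 90. The Synopsis adds that "scores will be analyzed as categorical variables using the Cochran-Mantel-Haenszel test", without naming a 0/1 cut.

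**Fissures.** The Synopsis and 13.1.4.1 list the difference between active and vehicle in the proportion of subjects with palm/sole fissures at Day 90, with number and pain in the same bracket. Section 13.1.4.3 then says: "For subjects who report having fissures, descriptive summaries of the number of fissures and pain related to fissures will also be presented by treatment group". The Synopsis carries the same restriction. Neither place says when the fissures must be present.

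**The concern.** A responder count at one time point and a difference in means over the period are different endpoints. They can lead to different conclusions from the same data. Section 10.3.1.2 cannot be set aside as loose description: Section 10.3.1 says scales are either established ones or defined in its subsections, and 10.3.1.1 uses the same sentence form for the primary endpoint. Section 15 ties the study report to the protocol-defined endpoints, so with both versions in force either could be presented as the VIIS result after unblinding.

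The cut itself is also doubtful. A score of 0 or 1 is a natural success rule on a single 0-4 scale. On a sum of four such scales it means something much stricter.

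For fissures, a summary by arm among subjects who have fissures at a visit conditions on an outcome that treatment can change. The arms within that subset are no longer the arms as randomised, and the summary can point the wrong way.

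**Working it through.** **1. The plan's own figure.** Four body areas (chest/abdomen, back, arms, legs), each scored 0-4: 4 x 4 = 16. This reproduces the stated maximum (Synopsis; footnote g of Table 2-1).

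**2. The definitions side by side.**
- Section 10.3.1.2: number of subjects at 0 or 1; Day 90/EOT; 16-point total. No analysis is named in Section 13.
- Synopsis: difference in means; Baseline through Day 90; 5-point scale by area with a 16-point total. MMRM.
- Section 13.1.4.1: difference in means; Baseline through Day 90; 5-point scale, total not mentioned. MMRM under 13.1.4.3.

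The logistic models in Section 13 cover IGA success (13.1.4.2), a 50% IGA reduction (13.1.4.3), and 2-grade changes in roughness and palm/sole score (13.1.4.5). None covers a VIIS responder.

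**3. What a total of 0 or 1 requires.** There are 5^4 = 625 possible profiles of four area scores.
- Total of 0 or 1: all four areas at 0 (1 profile), or three at 0 and one at 1 (4 profiles), giving 5 profiles.
- 0 or 1 in every area: 2^4 = 16 profiles, with totals up to 4.
- A subject at 1 in all four areas has total 4 and fails.

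These are counts of profiles, not probabilities.

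**4. Illustration of the responder rate.** The documents give no area-level distribution, so the values below are assumptions.
- Every area scored 0 or 1, with probability q of 0 and areas independent: P(total of 0 or 1) = q^4 + 4q^3(1 - q). For q = 0.2: 0.0016 + 0.0256 = 0.027. For q = 0.5: 0.0625 + 0.25 = 0.3125.
- Same q, but all four areas always equal: the total is 0 or 1 only when all are 0, so the rate is q, that is 20% and 50%.
- Some areas above 1, independent, P(0) = p0 and P(1) = p1: total of 0 or 1 = p0^4 + 4 p0^3 p1; every area 0 or 1 = (p0 + p1)^4. For (0.1, 0.5): 0.2% against 13%. For (0.5, 0.3): 21% against 41%.

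**5. Illustration of the fissure subset.** Constructed, 40 per arm. Vehicle has counts 0, 1, 2, 4 and 8 in 8 subjects each. Every active subject has 2 fewer, with a floor at 0, so the counts are 0, 0, 0, 2 and 6.
- All subjects: vehicle 8 x 15 / 40 = 3.0; active 8 x 8 / 40 = 1.6. Active is better.
- Subjects with fissures only: vehicle 120 / 32 = 3.75; active 64 / 16 = 4.00. Active looks worse.

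The reversal comes from the low counts reaching zero and leaving the subset. It shows what can happen, not what will.

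**The case against.** The strongest reply is that the plan already points to one answer. Two sections give the mean difference, it has an MMRM, and the responder version is never carried into Section 13. The 5-point label in 13.1.4.1 may be shorthand for the area scale, since the Synopsis uses the same label and then gives the total. This stands as far as it goes: a usable VIIS comparison exists, and a reader who infers that the plan has none goes further than the text allows. It does not remove a sentence that plainly names another quantity as the secondary endpoint, and this is a conflict within the protocol, not detail left for the SAP.

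A reader might also infer that the responder rate would be close to zero, even among subjects who meet the primary endpoint. The documents do not support that. The low figures depend on assumed probabilities and on independence between areas of one subject's skin; the independent case already reaches 31%, and full dependence gives up to 50%. The IGA is a separate global scale that includes roughness, so primary success does not translate into VIIS area scores.

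On fissures, a reader might infer that the arms are compared only among subjects whose fissures persist after treatment. The plan does not say so. Fissure presence is compared as a proportion with no such restriction, and the restricted summary is descriptive, additional and without a test. The opening sentence of 13.1.4.3 promises descriptive statistics for secondary endpoints generally, which may cover number and pain in all subjects. No time point is attached to having fissures, although they are assessed at every clinic visit. Pain is recorded per fissure, so describing it among those with fissures is natural. What remains is narrow: the only summary named specifically for number and pain is on a subset that treatment may alter.

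**Conclusion.** The VIIS contradiction holds on the text alone and needs no assumption. The protocol fixes two different endpoints under one name, leaves the scale incompletely stated in 13.1.4.1, and analyses only one of them. The mismatch between the 0/1 cut and a four-area sum is also exact: at least three areas must be at 0, and a subject at 1 throughout fails. How far the responder rate would fall is not known from the documents; the percentages above are illustrations.

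The consequence is moderate. The primary endpoint and the sample size are untouched. The issue is which VIIS result may be called the secondary endpoint, and it should be settled before unblinding.

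The fissure point is secondary. It matters if having fissures is judged at the visit being summarised, in which case the by-arm figures could mislead in either direction.

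**What to change.** - **Section 10.3.1.2:** replace the endpoint sentence with the mean-difference endpoint.
- **Synopsis, 10.3.1.2 and 13.1.4.1:** state in the same words that the VIIS score is the 0-16 total of four areas, analysed as change from Baseline through Day 90 by the MMRM in 13.1.4.3. Copying the present 13.1.4.1 wording into 10.3.1.2 would not be enough, because it does not name the total.
- **If a responder rate is kept:** define it as 0 or 1 in each of the four areas, and label it supportive.
- **Synopsis and 13.1.4.3, fissures:** summarise number and pain by arm over all ITT subjects, with an observed absence of fissures counted as 0 and a missing assessment kept as missing. State when fissures must be present for the fissure-only summary, and label that summary as descriptive and not a randomised comparison.

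The cost is protocol wording, with matching SAP text. Section 10.3.1.5 already collects presence, number and pain, and the VIIS is already scored by area, so no new data are needed.

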10.3.1.3 Individual Score for Roughness

The amount of roughness of the skin overall will be measured on a 5-point scale.

0	Clear	Smooth skin
1	Almost Clear	Hardly palpable roughness
2	Mild	Mild roughness (fine sand paper-like)
3	Moderate	Moderate, coarse roughness (coarse sand paper-like)
4	Severe	Very coarse skin (broken cornflakes-like)

10.3.1.4 Palm/Sole Assessment

Thickening of the skin on the palms and soles will be measured on a 5-point scale.

0	Clear	No thickening, no roughness, no fissure
1	Almost Clear	Only slight thickening, minimal to no roughness, no fissures
2	Mild	Some thickening, mild roughness on palpation, few fissures may be present
3	Moderate	Substantial and diffuse thickening, coarse roughness on palpation may be present, fissures may be present
4	Severe	Very thickened and rough skin, numerous fissures

10.3.1.5 Palm/Sole Fissuring Assessment

Fissuring will be assessed by recording the presence or absence of fissures, the number of fissures present, and the pain associated with each fissure. A fissure is a longitudinal and deep crack that separates the stratum corneum and may penetrate down to the dermis, causing pain and sometimes bleeding. The subject will assess pain associated with fissures as ranging from 0-3 (none, mild, moderate, severe).

10.3.1.6 Dermatology Life Quality Index

The DLQI is a dermatology-specific Quality of Life instrument. It is a simple 10-question validated questionnaire with 6 domains (symptoms and feelings, daily activities, leisure, work and school, personal relationships, and treatment); higher scores indicate poorer quality of life. The DLQI is the most frequently used instrument in studies of randomized controlled trials in dermatology.

10.3.1.7 EQ-5D Quality of Life Questionnaire

The EQ-5D is a standardized instrument developed by the EuroQol Group as a measure of health-related quality of life used in a wide range of health conditions and treatments. The EQ-5D consists of a descriptive system and the EQ visual analog scale (VAS).

The descriptive system comprises 5 dimensions: mobility, self-care, usual activities, pain/discomfort, and anxiety/depression. The EQ VAS records the subject's self-rated health on a vertical 0-100 VAS. This can be used as a quantitative measure of health outcome that reflects the subject's own judgment.

10.3.1.8 Ectropion Severity Score

The ESS has a maximum score of 8 points. A higher score indicates a worse ectropion. The score takes the severity of ectropion in terms of lateral and medial apposition, scleral show, conjunctival show, and roundness of the eye into account and gives an indication of the functional aspects involved in ectropion by scoring redness, excess tear film, and the position of the lacrimal punctum.¹⁴

Table 10-1: Ectropion Severity Score

	Points per Item		
	0	0.5	1
Lateral apposition	Nonaffected	—	Affected
Medial apposition	Nonaffected	—	Affected
Scleral show	No	≤1 mm	>1 mm
Conjunctival show	No	—	Yes
Excess tear film	No	—	Yes
Redness of the eye	No	—	Yes
Round canthus	No	—	Yes
Punctum lacrimale	Invisible	Emerging	Visible
Maximum score			8 points

Source: Korteweg SFS, Stenekes MW, van Zyl FE, Werker PMN. Paralytic Ectropion treatment with lateral periosteal flap canthoplasty and introduction of the ectropion severity score. *Plast Reconstr Surg Glob Open*. 2014;2(5):e151.

10.3.1.9 Photography Substudy

All sites that have photographic capability will take photographs as source data to support scoring at Baseline, Day 30, and Day 90. A central reader who will not be an investigator in the study will review the photographs to assess consistency of investigator scoring of LI severity as a quality check. Photographs may also be used for scientific publication purposes. Subjects will sign a separate, optional photographic informed consent form (ICF).

10.3.2 Clinical Pharmacology

10.3.2.1 Pharmacokinetic Analysis Methods

The pharmacokinetic characterization of drug concentrations for each dose to be profiled will use noncompartmental analysis (NCA).

10.3.2.2 Pharmacokinetic Parameters

Samples for PK will be drawn from all subjects at Baseline and at each clinic visit for trough values.

Subjects who provide written informed consent to participate in the optional PK substudy will provide blood samples for PK analysis predose on Day 1 and at 1, 2, 4, 8, 12, and 24 hours postdose on Day 1 and Day 30.

The PK parameter estimates will be completed using WinNonlin (Pharsight Corporation) software using the actual elapsed times from dose administration to sample collection (i.e., not nominal time).

Standard PK parameters assessed will include measures of the extent of absorption using estimates of the area-under-the-curve (AUC) and rate-of-absorption using the maximum concentration (C_{max}) and the time of C_{max} (T_{max}). Additional details of the parameters and their calculation and evaluation will be included in the statistical analysis plan (SAP).

Table 10-2 shows the PK parameters that will be computed for each subject for samples obtained over the planned sampling intervals.

Table 10-2: Pharmacokinetic Parameters

Parameter	Description of Parameter
C_{max}	Maximum (or peak) serum concentration
T_{max}	Time at which C_{max} is observed
$AUC_{(0-t)}$	Area under the plasma concentration-time curve from time 0 to the time of the last quantifiable plasma concentration
$AUC_{(0-inf)}$	Area under the plasma concentration-time curve from time 0 to infinity (if data permit)
$t_{1/2}$	Apparent first order terminal elimination half-life
λ_z	Apparent terminal phase rate constant (if data permit)

10.3.3 Sample Collection

Samples will be collected at the time points specified in the Schedule of Events (Section 2.2). Specimen preparation, handling, shipment, and storage for the complete blood count, chemistry, and urinalysis are described in the study laboratory manual. Finding veins in subjects with this disease can be challenging. Blood draws will be done at the corresponding study visits before application of the IP and should be 24 hours after IP application. Subjects must not apply the IP to the area where blood will be drawn within 24 hours before their next study visit to avoid contamination of the blood by IP that remained in the skin. For subjects in the PK substudy, a cannula should be placed before IP application and the cannula site may be occluded to prevent contamination with IP.

Actual PK sample times for subjects in the PK substudy will be recorded in the eCRF.

Blood

For subjects not in PK substudy:

The expected amount of blood to be drawn at each visit varies from approximately 6 mL to a maximum of 21 mL (Screening Visit only). The total amount of blood drawn for the study will be about 123 mL per subject, unless the subject takes part in the PK substudy.

For subjects in PK substudy:

For subjects who opt to participate in the PK substudy, extra blood samples will be drawn at Visit 2 and at Visit 4 for PK analysis. The amount of blood to be drawn per subject at each of these visits will be approximately 54 mL. For subjects taking part in the substudy, the total amount of blood drawn for the entire study will be approximately 195 mL.

Urine

Urinalysis will be performed at central laboratory. Dipstick and urine pregnancy tests will be conducted on site.

